number of PLWH participants in Stage 1A will be n=32. Additionally, we will conduct 4 FGDs with health workers at our study clinics. These FGDs will also have a maximum number of 8 participants per group, thus the maximum number of healthcare worker participants will be n=32. Finally, we will conduct up to 16 key informant interviews with policy officials and relevant program leaders.

Stage 1B: This stage will enroll n=320 participant who have hazardous alcohol use: n=160 will formally be enrolled in the RCT (participants who meet criteria for a moderate-to-severe AUD or have hazardous alcohol use plus comorbidities) and n=160 who will not be enrolled in the RCT but will receive the BI and will be tracked for follow-up in a cohort study (participants with hazardous use but do not have a moderate-to-severe AUD and have no comorbidities).

The primary endpoint of the pilot RCT is the difference in change in AUDIT score from baseline to 6-month follow-up between BI+CETA and BI alone (see assessments section below). We believe that an effect size of CETA  $\geq 0.5$  would be clinically significant and justify further investigation in a subsequent latter Stage trial. Further assuming  $\alpha=0.05$  and  $\beta=80\%$ , we will require a total sample size of 128 (n=64 per arm). To account for possible loss-to-follow-up/drop-out of 20% based on our previous studies with HIV-affected populations in Zambia, we will inflate the sample size to 160 (n=80 per arm). Based on Preliminary Studies, we anticipate that 20% of female and 40% of male patients at the study sites will report hazardous drinking and that 50% of hazardous drinkers will qualify for the RCT. Therefore, we expect to enroll n=320 hazardous drinkers to reach the RCT target sample size. There is no sample size calculation for cohort study participant; however, the anticipated sample of n=160 should be sufficient to detect even a small within-group change in outcomes after receipt of BI.

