Follow-up assessments. Alcohol and comorbidities will be assessed in all participants at 6 months (i.e., endline) after baseline. The ACASI questionnaire that was used at baseline will again be administered at this follow-up visit (i.e., the questionnaire at this visit is the same as at baseline). In addition to ACASI assessments, we will confirm self-reports of alcohol abstinence on the AUDIT by conducting a urine-based rapid alcohol biomarker test, ethyl glucuronide (uEtG). Finally, at the 6-month post-assessment, which coincides with a regularly scheduled clinic visit, we will extract relevant information from the client's HIV clinical record (this will be the same information that is collected at baseline), including: , (1) hepatitis B surface antigen, (2) most recent CD4+ count, (4) cumulative and past 6-month ART retention, defined by medication possession ratio (MPR; an objective pharmacy record metric that we have used previously) and (4) plasma HIV viral load (measured at CIDRZ Central laboratory using the Roche COBAS/Ampliprep platform). We will not collect any additional biospecimens for purposes of the study—all HIV-related data will be captured via chart extraction. To supplement retention data captured through MPR measurement, we will also assess visit adherence, the percentage of assigned pharmacy and clinical visits that were made (coming to clinic within 3 days).

Implementation data collection. We will conduct a mixed methods process evaluation with stakeholders involved in the CETA referral and treatment process, including follow-up FGDs and KIIs with participants from Stage 1A and CETA counselors. We will also conduct mixed methods interviews with approximately N=30 PLWH who participated in the Stage 1B pilot RCT. This will include a purposeful sample of PLWH from a range of ages and both sexes who did and did not complete the BI and CETA. Implementation factors to be explored will include: acceptability, appropriateness, reach, cost, feasibility, and sustainability and will explore the attitudes, thoughts, feelings, and barriers and facilitators related to implementation. Interviews will include an in-depth interview component and JHU quantitative implementation measures.

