*Analysis of CETA clinical monitoring data.* We will conduct longitudinal data analysis with CMF and TLFB daily estimates of drinking during CETA. Exploratory analysis will examine trajectories of weekly symptom change based on CMF score and number of drinks per day using spaghetti and scatter plots. We will explore the association between baseline client characteristics on symptom trajectories. We will use survival analysis to calculate the number of sessions required for 25%, 50%, and 75% of clients to achieve one or two standard deviation(s) in symptom improvement from baseline. We will also calculate the percentage of clients that achieve these changes by the end of treatment. Collectively, these analyses will provide insight into *when* symptoms change over the course of treatment, which may be useful in refining CETA in future studies.

*Analysis of HIV outcome data.* In both RCT and non-RCT participants, we will use a linear model to investigate changes to MPR during the period before and after the intervention and a logistic model for changes to the proportion with HIV viral suppression (defined as <1000 copies/ml, the standard in SSA). We will compare visit adherence between those randomized to BI+CETA versus BI alone. Because of the relatively small sample sizes in this pilot study, these data will be primarily descriptive; however, these data will inform a follow-up grant.

*Analysis of uEtG results.* The purpose of uEtG testing is to confirm abstinence and not to validate AUDIT scores >0. Based on Preliminary Studies we expect to identify 'under-reporters,' defined as participants who report abstinence on AUDIT or TLFB and test uEtG-positive. In a secondary analysis, we will exclude under-reporters and re-assess the impact of the intervention on alcohol use and other outcomes.

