The only biospecimen being collected in this study will be a urine ethyl glucuronide (ETG) test to confirm alcohol abstinence. In previous alcohol research conducted by our team in Zambia, we have found that it is important to compare self-reported alcohol use to an objective biomarker. This urine specimen will only be collected at one timepoint among cohort and RCT participants: at the 6-month post-baseline assessment. The test requires the participant to provide a small urine sample (appx. 100ml). During the study visit we will provide participants with a urine cup and ask them, in a private bathroom at the clinic, to provide us with a 100ml sample of urine. Following the sample collection, a study assessor will insert a dipstick into the sample and within 1 minute the test provides a qualitative (positive/negative) result for alcohol consumption within the past 2-5 days.

We will provide participants with results of the EtG test at the visit. No additional tests except the dipstick will be conducted with the sample. Following testing, the sample will be destroyed. We have used EtG tests previously with similar patient populations and it was found to be feasible and acceptable ([name] et al., 2018).

3. If genetic/genomic analyses are planned, address whether the data will be contributed to a GWAS or other large dataset. Address returning unanticipated incidental genetic findings to study participants.

N/A

4. If clinical or laboratory work will be performed at JHU/JHH, provide the JH Biosafety Registration Number.

N/A

5. If you will perform investigational or standard diagnostic laboratory tests using human samples or data, clarify whether the tests are validated and/or the lab is certified (for example is CLIA certified in the U.S.). Explain the failure rate and under what circumstances you will repeat a test. For all human testing (biomedical, psychological, educational, etc.), clarify your plans for reporting test results to participants and/or to their families or clinicians. Address returning unanticipated incidental findings to study participants.

The urine dipstick ETG test has been FDA-approved and validated.

Urine dipstick results (positive or negative) for ETG will be discussed with participants as soon as they are available (within 1 minute of sample collection).

6. If your study involves medical, pharmaceutical or other therapeutic intervention, provide the following information:

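### A single uEtG test with a 2-5 day window cannot confirm longer abstinence, and the under-reporter rule does not secure a matching self-report in both arms

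*Combined protocol and SAP*

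**What the plan says.** - **Primary endpoint (Section III.B).** "The primary endpoint of the pilot RCT is the difference in change in AUDIT score from baseline to 6-month follow-up", compared between BI+CETA and BI alone. The AUDIT is self-reported by ACASI, and participants learn their arm when the envelope is opened after baseline.
- **Biomarker (Section V, Follow-up assessments).** "we will confirm self-reports of alcohol abstinence on the AUDIT by conducting a urine-based rapid alcohol biomarker test". The same paragraph makes the 6-month questionnaire identical to the baseline one. Baseline data collection names four instruments: AUDIT, CES-D, HTQ and ASSIST.
- **Specimen (Section V, item 5.2 on biospecimens).** "This urine specimen will only be collected at one timepoint among cohort and RCT participants", namely the 6-month visit. No AUDIT limit is set on who gives urine, and "the test provides a qualitative (positive/negative) result for alcohol consumption within the past 2-5 days".
- **Use in analysis (Analysis of uEtG results).** "The purpose of uEtG testing is to confirm abstinence and not to validate AUDIT scores >0". An under-reporter is someone with a positive test who reported abstinence on either the AUDIT or the TLFB. A secondary analysis drops these participants and re-estimates the treatment effects.
- **TLFB.** Clinical monitoring data collection describes a past 7-day TLFB completed only within CETA sessions, and states that BI-alone and cohort participants do not complete it. Analysis of ACASI outcome data nevertheless lists a past 30-day TLFB as a secondary outcome.
- **Timeline (Table 4).** A post-treatment row with uEtG stands apart from the 6-month row, although item 5.2 allows one collection only.

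**The concern.** The primary outcome is self-report in people who know their allocation, and the dipstick is the only objective check on reported drinking. Two features weaken it. First, a yes/no result for the last few days is described as confirming abstinence, which is a longer claim than the test can carry. Someone who drinks but abstains for some days before a scheduled visit tests negative. Second, a biomarker tests a self-report only when both refer to the same days. The rule relies on the AUDIT, whose recall period the documents do not state, or on a TLFB that one section gives to a single arm. Urine is collected from everyone, yet the plan sets aside its use for checking AUDIT scores above 0.

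At stake is the credibility of the secondary analysis that excludes under-reporters. If the chance of being flagged differs by arm, that analysis cannot reassure a reader about the self-reported result, and it could itself shift the comparison.

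**Working it through.** **1. The plan's own figures.** The documents give no sensitivity for the dipstick, no under-reporting rate and no drinking frequency at follow-up. The one relevant stated figure is the sample size. With d = 0.5, two-sided alpha 0.05 (sidedness is not stated; one-sided would give about 100 in total) and 80% power, a two-sample t-test needs 63.77, so 64 per arm and 128 in total. Then 128 / (1 - 0.20) = 160. Both stated totals reproduce.

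**2. What a negative test covers.** Taking 6 months as 182 days, 2/182 = 1.1% and 5/182 = 2.7% of follow-up.

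**3. Chance that one test detects a false abstainer.** The window w = 2 or 5 days is from item 5.2. The rest is assumed: k drinking days placed at random in 28 days, and a perfect assay within its window. Then P = 1 - C(28-w, k) / C(28, k). For k = 1 this is 2/28 = 0.071 and 5/28 = 0.179.

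| Drinking days in 28 | 2-day window | 5-day window |
|---|---|---|
| 1 | 7% | 18% |
| 2 | 14% | 33% |
| 4 | 27% | 57% |
| 8 | 50% | 84% |

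Treating days as independent, P = 1 - (1-p)^w with daily drinking probability p, gives similar values: 7-16% at one day a month, 27-54% at one a week, 49-81% at two a week, 82-99% at four a week. Detection passes 50% at 7 x (1 - 0.5^(1/w)) days a week, which is 2.05 for w = 2 and 0.91 for w = 5. Skipping days before the visit, or an imperfect assay, would lower all of these.

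**4. Share of all under-reporting detected.** Let s be the share of under-reporters who claim full abstinence (assumed), and count partial under-reporters as undetected. The share detected is s x P, using the independent-days model.

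| s | 1 day/week | 2 days/week | 4 days/week |
|---|---|---|---|
| 0.5 | 13-27% | 24-41% | 41-49% |
| 0.75 | 20-40% | 37-61% | 61-74% |
| 1 | 27-54% | 49-81% | 82-99% |

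The answer falls on either side of one half, depending on two inputs that the documents do not supply.

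**5. The rule by arm.** Take two participants with AUDIT above 0 and a positive dipstick at 6 months.
- In BI+CETA, a TLFB reporting no drinking is enough to flag the participant.
- In BI alone, under the Clinical monitoring text, no TLFB exists, so an identical participant cannot be flagged.

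The CETA form is not matched in time either. Sessions are weekly for 6-12 weeks, and a participant must start within one month. At that pace the last session falls by about week 4 + 12 = 16, roughly 10 weeks before a visit at week 26. A truthful zero in the last session followed by later drinking would count as under-reporting.

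Even the AUDIT route can differ by arm, because detection depends on drinking frequency, which CETA aims to change. If false abstainers drank on 4 days in 28 in one arm and 8 in the other, 27-57% against 50-84% would be flagged (an illustration, not a forecast).

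**6. The exclusion.** Dropping flagged participants selects on a post-randomization result. Starting from 64 per arm with equal exclusion in both arms, power at d = 0.5 falls to 78% (5% excluded), 76% (10%), 71% (20%) or 65% (30%).

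**The case against.** The plan states the window openly, limits the purpose of the test and uses it in one secondary analysis. It creates no analysis category of confirmed abstainers; only positive results are acted on. ACASI hides answers from the interviewer, follow-up is done by a different assessor, assessors are blinded, and both arms receive counselling on alcohol. A 30-day TLFB given to everyone at 6 months would cover the test window, including for people with AUDIT above 0. And a new question would not raise the detection figures in step 3: a rare drinker, or one who skips days, still tests negative.

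Much of this stands. It keeps the point away from the primary analysis and limits what the fix can promise. It does not settle the matter. Disclosing the window does not make the word confirm accurate. ACASI and blinded assessors do not remove a participant's own reasons for under-reporting. The 30-day TLFB is listed as an outcome but is absent from the named ACASI measures, and another section excludes it for BI-alone participants, so a matched self-report in both arms is possible but not assured.

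**Conclusion.** A single 2-5 day test cannot confirm abstinence over a longer period, and the under-reporter rule does not guarantee a window-matched self-report in both arms. As written it could flag participants differently by arm and then exclude them. Detection of false abstainers ranges from 7-18% at 1 drinking day in 28 to 50-84% at 8, assuming random drinking days and a perfect assay. The true extent of missed under-reporting is not derivable from the documents. The primary AUDIT analysis does not use uEtG, so this limits the check on self-report and not that analysis itself.

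Three stronger readings are tempting, and the documents do not support them:
- **That the test misses most under-reporting.** This holds if at least half of under-reporters admit some drinking, or if false abstainers drink less than about one to two days a week. It fails for frequent drinkers who mostly deny all use.
- **That urine is ignored for everyone with AUDIT above 0.** The TLFB alternative in the rule can flag such a participant, though on one section's account only in the CETA arm.
- **That CETA participants under-report more.** This is plausible, but nothing in the documents shows it.

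**What to change.** 1. Reconcile Baseline data collection, Clinical monitoring data collection, Follow-up assessments, Analysis of ACASI outcome data and Analysis of uEtG results on who completes a TLFB, over what period and when. Also reconcile the extra uEtG row in Table 4 with the single collection in item 5.2.
2. In the 6-month ACASI, before the urine test, ask all participants in both arms the same recent-drinking question: the 30-day TLFB if it is kept, otherwise one item on any alcohol in the past 5 days or on days since the last drink.
3. Define under-reporting as denying alcohol within the test window with a positive uEtG, whatever the AUDIT score, and report that proportion by arm.
4. Describe a negative test as no drinking detected in the past 2-5 days, not as confirmed abstinence.

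Cost: under a minute of participant time if the single item is used, and a weaker claim for a negative test. No extra specimen or visit is needed, and the sample size stays at 160. The change gives both arms the same definition and uses urine already collected. Rare drinkers, those who skip days before the visit, and understated quantity remain undetected.

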Baseline data collection. The baseline assessment will be conducted via ACASI. The participant will first complete the Alcohol Use Disorders Identification Test (AUDIT) to assess eligibility into the study. The ACASI will automatically alert the assessor if the participant is eligible based on the hazardous alcohol use criteria. If eligible, the participant will complete the remaining measures: (1) Center for Epidemiological Studies-Depression Scale (CES-D); (2) Harvard Trauma Questionnaire (HTQ); and (3) the Alcohol, Smoking, and Substance Involvement Screening Test (ASSIST). All of these measures have previously been translated and used by our team in Zambia and the AUDIT, CES-D, and ASSIST measures have been formally validated. A research assistant will be available if there are any challenges with the ACASI. Additionally, we will use HIV clinic files to extract HIV-related data. These data are captured as part of HIV routine care in Zambia and include: (1) ART initiation date, (2) hepatitis B surface antigen, (3) most recent CD4+ count, (4) cumulative and past 6-month ART retention, defined by medication possession ratio (MPR; an objective pharmacy record metric that we have used previously) and (5) plasma HIV viral load (measured at CIDRZ Central laboratory using the Roche COBAS/Ampliprep platform).

Secondary eligibility criteria for the RCT. Following completion of the baseline assessment, ACASI will automatically alert the assessor if the participant is eligible for the pilot RCT via a built-in algorithm. Criteria for the RCT will be (a) AUDIT scores that indicate a moderate-to-severe AUD ( $\geq 12$  for women;  $\geq 16$  among men) and/or (b) meeting validated symptom criteria for depression ( $\geq 16$  on CES-D), trauma/anxiety ( $\geq 2.5$  on HTQ), and/or substance use ( $\geq 27$  for any non-tobacco substance on ASSIST).

Randomization. Participants eligible for the pilot RCT will be randomized 1:1, stratified by sex, to receive the BI alone or BI+CETA. Participants who are NOT eligible for the pilot RCT will be provided with a BI but will not be randomized.

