[Tracking of treatment uptake and completion.](#) We have developed rigorous and sophisticated participant tracking systems through our previous Zambia studies. We will systematically track throughout the course of the study: (1) the number of participants who successfully complete and decline BI; (2) the number of participants who successfully link to CETA, defined as attending the first CETA session; (3) the amount of time counselors dedicate to client tracking/retention; and (4) the number of clients who successfully complete CETA. Counselors will attempt to track clients to the extent that this would be practical in a real-world setting.

[Clinical monitoring data collection.](#) During CETA sessions, the counselor will administer a brief clinical symptom checklist (Client Monitoring Form; CMF) and a past 7-day Alcohol TLFB. These data guide clinical care by informing the choice of CETA elements to be delivered in session and will also be used in analyses. These forms will only be administered to CETA participants during their CETA sessions. (Neither RCT participants randomized to the BI alone nor Cohort study participants will complete the TLFB).

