Study Phase	Activity	Year 1				Year 2				Year 3			
		Q 1	Q 2	Q 3	Q 4	Q 1	Q 2	Q 3	Q 4	Q 1	Q 2	Q 3	Q 4
Planning	Study protocol finalization and ethical approval												
	Staff hiring and site preparation												
	Training of qualitative data staff												
Stage 1A	Focus groups and key informant interviews												
	Adaptation of CETA for PLWH												
	Development of CETA protocol in HIV care based on Stage 1A												
	CETA/mhGAP-IG trainings, assessor trainings, M&E trainings												
Stage 1B	CETA pilot cases												
	Recruitment, consent, screening and baseline assessments (ACASI, HIV)												
	Interventions active												
	Post-treatment assessments (ACASI, UEtG)												
	6-month outcomes assessment (ACASI, UEtG, HIV outcomes via chart review)												
Analysis, dissemination, and next steps	Implementation data collection (PLWH, clinic staff, policy officials)												
	Data analysis												
	Report/manuscript writing and dissemination at conferences												
	Preparation and submission of follow-up R01												

- Provide a brief data analysis plan and a description of variables to be derived.

*Analysis of treatment uptake and completion.* We will estimate a logit model with a binary outcome (1=completer; 0=non-completer) to assess predictors of treatment completion. Predictors will be demographic (e.g., sex, age), clinical (e.g., symptom severity), and structural (e.g., distance from clinic) level factors.

*Analysis of ACASI outcome data.* Analyses will be intent-to-treat. AUDIT score, along with other continuous secondary outcomes (Past 30-Day TLFB [% days drinking and mean drinks per day], CES-D, HTQ, ASSIST scores) will be modelled with linear mixed models. Fixed effects will include treatment arm (0=BI; 1=BI+CETA), time (0=Baseline; 1=6-months post-baseline), and interaction terms between treatment arm

and time. This will allow estimation of the mean difference in change in score between arms and 95% confidence intervals. Cohen's D will be calculated to estimate effect size. Covariates will be included if they differ meaningfully at baseline or predict significant change in the outcome. For dichotomous outcomes or non-normally distributed continuous outcomes, generalized linear mixed effects models will be estimated. Paired t-tests will be used to assess within group change among the non-Pilot RCT hazardous drinkers.

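### The past-30-day TLFB is analysed between arms and used to flag under-reporters, but the only TLFB scheduled is a past-7-day form in CETA sessions

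*Combined protocol and SAP*

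**What the plan says.** The analysis plan uses the TLFB in two between-arm roles.

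- Analysis of ACASI outcome data names "Past 30-Day TLFB [% days drinking and mean drinks per day], CES-D, HTQ, ASSIST scores" as intent-to-treat secondary outcomes. They enter a linear mixed model with arm, time (baseline and 6 months) and arm-by-time.
- Analysis of uEtG results sets up a secondary analysis that drops under-reporters, "defined as participants who report abstinence on AUDIT or TLFB and test uEtG-positive".

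The collection sections of V. Study Procedures describe something else.

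- Clinical monitoring data collection has the counselor give "a past 7-day Alcohol TLFB" along with the symptom checklist. It continues: "These forms will only be administered to CETA participants during their CETA sessions", and then "Neither RCT participants randomized to the BI alone nor Cohort study participants will complete the TLFB".
- Baseline data collection starts with the AUDIT and then says "If eligible, the participant will complete the remaining measures". The measures that follow are the CES-D, HTQ and ASSIST.
- Follow-up assessments says "The ACASI questionnaire that was used at baseline will again be administered at this follow-up visit". On the urine test it says "we will confirm self-reports of alcohol abstinence on the AUDIT" and does not mention the TLFB.

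**The concern.** An arm-by-time contrast needs the outcome in both arms at both visits. The analysis section assumes a 30-day TLFB that no collection section schedules. The one TLFB that is scheduled differs in recall period (7 days, not 30), mode (counselor, not ACASI), population (BI+CETA only) and timing (treatment sessions, not baseline and 6 months).

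If staff follow the collection text, the two drinking-quantity outcomes cannot be compared between arms, and baseline values that were not collected cannot be recovered.

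The under-reporter rule has a related problem. If session forms were used to apply it, the TLFB criterion could flag people in the BI+CETA arm only. Everyone it removed would have a positive urine test at 6 months, so one-sided removal would tend to flatter BI+CETA in an analysis meant to re-test the intervention effect.

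**Working it through.** **The plan's own figure.** III. Study Design, part B, sizes the RCT on the AUDIT with d = 0.5, alpha 0.05 and 80% power. A two-sided t-test calculation gives 63.77, so 64 per arm and 128 in total. Allowing for 20% dropout, 128 / (1 − 0.20) = 160, or 80 per arm. This reproduces the plan and does not depend on the TLFB. It supplies the denominators below.

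**Coverage of the mixed model, taking the collection sections as written.**

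| Measure | BI, baseline | BI, 6 months | BI+CETA, baseline | BI+CETA, 6 months | Cells |
|---|---|---|---|---|---|
| AUDIT | yes | yes | yes | yes | 4 of 4 |
| CES-D, HTQ, ASSIST (each) | yes | yes | yes | yes | 4 of 4 |
| 30-day TLFB | no | no | no | no | 0 of 4 |

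The BI entries for the TLFB rest on the sentence excluding BI-alone participants (0 of 80). The absence at baseline and 6 months in both arms (0 of 160) is inferred from the listed battery and from the statement that the two questionnaires are the same. With empty cells, neither the arm effect nor the arm-by-time effect can be estimated. Counted as % days drinking, mean drinks per day, CES-D, HTQ and ASSIST, 2 of 5 secondary measures are affected; by instrument it is 1 of 4.

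**Session TLFB against the urine test.** Inputs:

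- CETA lasts 6–12 weeks and starts within 1 month of enrolment or not at all (Interventions).
- The urine test is done once, at 6 months, and detects drinking in the past 2–5 days (the biospecimen answer in V. Study Procedures).
- 1 month = 30.4 / 7 = 4.34 weeks; 6 months = 6 × 30.4 / 7 = 26.06 weeks.

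Gap = 26.06 − start week − length of treatment:

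- Start at week 0, 6 weeks: 26.06 − 0 − 6 = 20.1 weeks
- Start at week 0, 12 weeks: 26.06 − 0 − 12 = 14.1 weeks
- Start at week 4.34, 6 weeks: 26.06 − 4.34 − 6 = 15.7 weeks
- Start at week 4.34, 12 weeks: 26.06 − 4.34 − 12 = 9.7 weeks

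If sessions run to schedule, the last session form precedes the urine test by roughly 10–20 weeks. A 7-day recall that old cannot be checked against a 2–5 day window.

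**The case against.** The best counter-reading is that the exclusion sentence follows a reference to the session forms and means only the 7-day form. A separate 30-day TLFB would then sit inside ACASI and simply be missing from the baseline list. That list may well be incomplete: the screening section says ACASI also collects demographics, which the list leaves out, and distance from the clinic is a planned predictor that no collection section mentions. This is a fair reading, and it means the loss of the outcomes is conditional. It does not remove the contradiction. The exclusion sentence says the TLFB without qualification, no section lists a 30-day version, and on this reading the battery and the exclusion sentence would still need correcting.

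Other points on that side:

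- The AUDIT criterion of the under-reporter rule works in both arms at 6 months. That stands; only the TLFB criterion is defective.
- No section proposes using session forms for that rule. Also true, so the differential exclusion and the 10–20 week gap apply only if someone did.
- Counting weekly sessions from the first one puts the last session a week earlier, for a gap of about 11–21 weeks. Sessions may also slip. Neither changes the conclusion.
- The Table 4 timeline has a post-treatment line with ACASI and the urine test, separate from the 6-month line. This conflicts with the single urine timepoint on which the gap calculation relies, and should be reconciled too. It supplies no TLFB.

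**Conclusion.** The collection and analysis sections contradict each other, and nothing in the document resolves it. That conclusion is firm.

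The size is conditional. If the collection sections govern, and the listed battery is complete, the between-arm TLFB analysis has no data in any of its four cells, and the TLFB part of the under-reporter rule could operate in BI+CETA only. If a 30-day ACASI TLFB was intended, the defect is an omitted instrument and an exclusion sentence that is too broad.

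On either reading the effect is limited to secondary outcomes and one secondary analysis. The AUDIT primary analysis, the sample size, the CES-D, HTQ and ASSIST analyses and the CETA-only trajectory analysis are untouched, and Hypothesis 1 can still be tested on the AUDIT and the comorbidity scales. It should be fixed, but it does not threaten the trial's main result.

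**What to change.** Choose one before the first participant is enrolled.

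**(a) Collect it.**

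- Add a past-30-day TLFB to the ACASI battery for both RCT arms, at baseline (before the envelope is opened) and at 6 months. List it under Baseline data collection and Follow-up assessments.
- Limit the exclusion sentence to the 7-day session form.
- State whether cohort participants complete it. The battery precedes the RCT/cohort split, and the Stage 1B overview promises cohort data on the same outcomes as the RCT.
- In the under-reporter rule, name the 6-month 30-day TLFB.

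Cost: a self-administered module must be prepared, since the plan describes only a counselor-given form. The document gives no TLFB duration. Assuming 5–15 minutes, it adds 5/120 to 15/120, about 4–13%, to an initial visit of up to 120 minutes, and 5/45 to 15/45, about 11–33%, to a follow-up visit of about 45 minutes.

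**(b) Drop it from the comparison.**

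- Remove the TLFB from the between-arm model.
- Define under-reporters by AUDIT-reported abstinence with a positive urine test, which matches Follow-up assessments.
- Keep the 7-day form as a descriptive measure under Analysis of CETA clinical monitoring data.

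Cost: wording edits in two analysis paragraphs, and the loss of the only listed between-arm outcomes expressed in drinking days and drinks per day.
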